6.2.4 Definitions of dose limiting toxicities (DLTs)

A dose-limiting toxicity (DLT) is defined as an adverse event or abnormal laboratory value of CTCAE Grade ≥ 3 assessed as unrelated to disease, disease progression, inter-current illness, or concomitant medications that occurs within the first two cycles of treatment with the combination treatment and meets any of the criteria included in [Table 6-3](#).

Emerging data from the new field of immune-immune combination studies suggest that some immune-related adverse events have a prolonged latency ([Wolchok 2013](#)). As such, the DLT window for the combination cohort in this trial is extended to the length of two cycles or 42 days.

National Cancer Institute Common Terminology Criteria for Adverse events (NCI CTCAE) version 4.03 will be used for all grading. For the purpose of dose-escalation decisions, DLTs will be considered and included in the BLRM.

The investigator must notify the Sponsor immediately of any unexpected CTCAE Grade ≥ 3 adverse events or laboratory abnormalities. Prior to enrolling patients into a higher dose level, CTCAE Grade ≥ 2 adverse events will be reviewed for all patients at the current dose level.

DLTs include any adverse event of CTCAE Grade 3 or higher occurring in the first two cycles of treatment during the Phase Ib dose escalation part of the study, for which relationship to study treatment cannot be ruled, with the exceptions defined in [Table 6-3](#).

Table 6-3 Criteria for defining dose-limiting toxicities

For the purpose of dose escalation and cohort expansion, DLT will be defined as follows: Any Grade 4 AEs will be considered DLTs with the exception of:
Neutropenia lasting ≤ 5 days that is not associated with fever or other clinical symptoms.
Lymphopenia or leukopenia at any grade
Any Grade 3 AEs will be considered DLTs with the exception of:
Electrolyte abnormalities that are not associated with clinical sequelae and are corrected to \leq Gr1 with appropriate management or supplementation within 72 hours of onset.
Infusion reaction that resolves to \leq Grade 1 within 6 hours.
Nausea and vomiting persisting for < 2 days with optimal anti-emetic therapy.
Thrombocytopenia without significant bleeding.
Diarrhea persisting for < 2 days with optimal anti-diarrhea therapy.
Hypertension persisting < 7 days with optimal therapy.
Infection or fever in the absence of neutropenia persisting < 7 days.
Rash or photosensitivity persisting < 7 days after treatment.

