Fatigue lasting < 7 days.
Immune-related adverse events persisting at Grade3 < 7 days after treatment with corticosteroids.
*CK elevation without associated muscle damage per investigator discretion
*Isolated AST elevations (without bilirubin or ALT elevations \geq Grade 1)
The following Grade 2 AEs will be considered as DLTs:
Total bilirubin $> 2 \times$ ULN with \geq CTCAE Grade 2 AST/ALT.

Pneumonitis persisting > 7 days despite treatment with corticosteroids.
Eye pain or reduction of visual acuity that does not respond to topical therapy and does not improve to Grade 1 severity within 2 weeks of the initiation of topical therapy OR requires systemic treatment.
Other clinically significant toxicities, including a single event or multiple occurrences of the same event may be considered as DLT's.
* MCS110 treatment results in CK and AST elevations without any association to muscle damage (Radi 2011). The CK/AST elevations are caused by reduced clearance rate from the circulation due to the diminished numbers of macrophages (Kupffer cells) in the liver (Section 1.2.2.1).

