6.3 Dose modifications

6.3.1 Dose modification and dose delay

For patients who do not tolerate the protocol-specified dosing schedule, dose adjustments are permitted in order to allow the patient to continue the study treatment, except during the first two cycles when dose modifications are only allowed if the patient experiences a DLT. The following guidelines need to be applied:

- If a patient experiences an AE meeting the criteria for DLT as outlined in Section 6.2.4, treatment should be withheld. Dose modifications for toxicities related to the study medication are summarized in Table 6-4. Following resolution of the toxicity to Grade 1 or to the patient's baseline value, the patient may resume study treatment at a lower dose level than is being tested at that time (on the same dosing schedule), if there is no evidence of disease progression as per irRC. A decision to resume treatment following the occurrence of a DLT is at the discretion of the Investigator. Following an AE meeting criteria for DLT, if a patient resumes study treatment, it should be at the next lower dose level. Dose reductions to doses below MCS110 0.3mg/kg / PDR001 100 mg Q3W are not permitted. If more than 2 consecutive doses have to be skipped due to study treatment-related toxicities, then the patient must be discontinued from the study unless the patient experiences clinical benefit in the opinion of the investigator. In this case, treatment can be continued at a dose agreed by Novartis and the investigator.
- For clinical management of suspected immune-related events, reference to consensus management guidelines is recommended such as those provided in the National Comprehensive Cancer Network (NCCN) Guidelines for the Management of Immunotherapy-Related Toxicities (available at : https://www.nccn.org/professionals/physician_gls/default.aspx#immunotherapy), the American Society for Clinical Oncology clinical practice guideline for Management of Immune-Related Adverse Events in Patients Treated With Immune Checkpoint Inhibitor Therapy (Brahmer 2018) or the European Society for Medical Oncology (ESMO) Clinical Practice Guidelines for Management of Toxicities from Immunotherapy (Haanen 2017). Note that in general, study treatment should be interrupted for grade 3 and 4 toxicities and for a subset of lower grade toxicities.

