- Consider early referral to specialists with expertise in the diagnosis and management of immune-related AEs to thoroughly investigate events of uncertain etiology.
- Events not included in the study protocol or the reference guidance documents should be managed per institutional preference.

- If one of the study drugs is discontinued the patient may continue with the remaining study drug, if the investigator considers it to be in the patient's best interest. The dose of the remaining study drug must be agreed by Novartis and the investigator.

Patients who discontinue the study treatment for a study related AE or a study-related abnormal laboratory value must be followed as described in [Section 6.3.2](#).

Table 6-4 Dose modification for drug related toxicities

Toxicity	Dose Adjustment Rules*
Hematology	
Neutropenia (ANC)	
Grade 3 or Grade 4.	Hold study treatment. Upon resolution to \leq Grade 2 or baseline within \leq 7 days, resume study treatment without dose modification, after discussion with the Novartis Medical Monitor
Febrile neutropenia	
Grade 3 or Grade 4	Hold study treatment. Upon resolution of fever and improvement of neutropenia to \leq Grade 2 or baseline, resume study treatment without dose modification, after discussion with the Novartis Medical Monitor.
Thrombocytopenia	
Grade 3	Hold study treatment. Upon resolution to \leq Grade 2 or baseline, resume study treatment without dose modification. For Grade 3 associated with major bleeding, discontinue study treatment.
Grade 4	Discontinue study treatment.
Anemia	
Grade 3 or Grade 4	Hold study treatment. Upon resolution to \leq Grade 2 or baseline within \leq 7 days, resume study treatment without dose modification.
Lymphopenia	
Any grade	Treatment-related lymphopenia does not require study treatment hold or discontinuation.
Gastrointestinal	
Diarrhea/colitis*	
Grade 1	May continue study treatment without dose modification. Manage per institutional standard guidelines which should include anti-diarrheal treatment, consideration of corticosteroid therapy, and hydration.
Grade 2	Hold study treatment. GI consultation. Upon resolution to \leq Grade 1 and tapering of steroid requirement to \leq 10 mg prednisone per day, resume study treatment without dose modification after discussion with the Novartis Medical Monitor.

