Grade 3	Hold study treatment. GI consultation. Upon resolution to \leq Grade 1 and tapering of steroid requirement to \leq 10 mg prednisone per day, consider resuming study treatment after discussion with the Novartis Medical Monitor.
Grade 4	Discontinue study treatment.

Toxicity	Dose Adjustment Rules*
Hepatic (AST and/or ALT elevation)	
Grade 2 AST and/or ALT	Hold study treatment. Manage per institutional practice. Upon resolution to \leq Grade 1 or baseline, consider resuming study treatment without dose modification.
Grade 2 transaminitis with bilirubin $>1.5 \times$ ULN (unless Gilbert's syndrome)	Discontinue study treatment.
Grade 3 AST and/or ALT	Hold study treatment. Manage per institutional practices. Upon resolution to \leq Grade 1 or baseline within 7 days, consider resuming study treatment without dose modification after discussion with the Novartis Medical Monitor. Otherwise, discontinue study treatment
Grade 4 AST and/or ALT	Discontinue study treatment.
Isolated total bilirubin elevation**	
Grade 2	Hold study treatment. Upon resolution to \leq Grade 1 or baseline, may continue study treatment without dose modification.
Grade 3	Hold study treatment. Upon resolution to \leq Grade 1 or baseline, may consider resuming study treatment after discussion with the Novartis Medical Monitor.
Grade 4	See footnote**. Otherwise, discontinue study treatment.
Asymptomatic amylase and/or lipase elevation***	
Grade 3 or Grade 4, not associated with symptoms or clinical manifestations of pancreatitis***	Continue study treatment. If levels do not resolve to \leq Grade 2 within \leq 14 days after the initial report, hold study treatment. Upon resolution to \leq Grade 2, may resume study treatment without dose modification, after discussion with the Novartis Medical Monitor.
Pancreatitis	
Grade 2 / radiologic evidence	Hold study treatment. Manage per institutional practice. Upon resolution to \leq Grade 1, may resume study treatment without dose modification, if no clinical evidence of pancreatitis and after discussion with the Novartis Medical Monitor.
Grade 3-4	Discontinue from treatment.
CK elevation	

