Grade 3-4	Monitor CK-MB isoenzyme, troponin (I or T), and creatinine. 
 • If CK-MB and troponin (I or T) are normal, creatinine $\leq 1.5 \times$ baseline and patient asymptomatic, continue treatment. • If CK-MB and troponin (I or T) are abnormal or creatinine ($> 1.5 \times$ baseline and $> \text{ULN}$) or patient symptomatic, delay treatment and explore alternative causes for elevated CK (for example myositis and rhabdomyolysis) according to local guidelines. 
After recovery of CK-MB, troponin (I or T) and creatinine to Grade 1 or baseline, restart treatment. Decrease MCS110 1 dose level.

Cytokine Release Syndrome (CRS)	
Grade 2	See instructions for Grade 2 Infusion Reaction.

Toxicity	Dose Adjustment Rules*
Grade 3 and Grade 4	Discontinue study treatment. Follow-up CRS as per institutional guidelines. Take blood for cytokine measurements as specified in Section 7.2.2.5.5 Laboratory evaluations.
Renal (creatinine)	
Grade 2	Hold study treatment. Consider resuming study treatment without dose modification upon resolution to \leq Grade 1 with appropriate management..
Grade 3 or 4	Discontinue study treatment.
Endocrine	
Hypothyroidism or hyperthyroidism	
Grade 2	May continue study treatment without dose modification. Management according to institutional practice.
Grade 3	Hold study treatment. Upon resolution to Grade \leq 1 with appropriate management, may resume study treatment without dose modification.
Grade 4	May resume therapy following resolution or control with physiologic hormone replacement.
Other endocrine disorders	
Grade 2 and Grade 3	Hold study treatment. Upon resolution to Grade \leq 1 with appropriate management, may resume study treatment without dose modification.
Grade 4	Hold study treatment. Grade 4 treatment-related endocrinopathies, such as adrenal insufficiency, adrenocorticotrophic hormone (ACTH) deficiency, hyper- or hypothyroidism, or glucose intolerance, which resolve or are adequately controlled with physiologic hormone replacement (corticosteroids, thyroid hormones) or glucose-controlling agents, respectively, may not require discontinuation after discussion with and approval from the Novartis Medical Monitor.
Pulmonary (pneumonitis)	
Grade 1	Consider study treatment hold. Manage per institutional practice. Consider resuming study treatment upon radiographic evidence of improvement.

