Grade 2	Consider study treatment hold, at Investigator discretion. Upon resolution to ≤ Grade 1, resume study treatment without dose modification.
Grade 3	Hold study treatment. Upon resolution to ≤ Grade 1, resuming study treatment must be discussed with the Novartis Medical Monitor.
Grade 4	Discontinue from treatment.
*Delay: treatment may be delayed for 7 days due to AEs. If a scheduled dose of ongoing study drugs is delayed longer than 7 days due to an unresolved AE, the administration should be skipped and treatment resumed at a lower dose level (if meeting the criteria for DLT) at the next scheduled dose (Section 6.1.1). Treatment: refers to both study drugs, unless one has been discontinued.	

Toxicity	Dose Adjustment Rules*
**Note: If Grade 3 or 4 hyper-bilirubinemia is due to the indirect (non-conjugated) component only, and hemolysis as the etiology has been ruled out as per institutional guidelines (e.g., review of peripheral blood smear and haptoglobin determination), then delay study treatment until resolved \leq Grade 1, and resume study treatment at the discretion of the investigator.	
***Note: A CT scan or other imaging study to assess the pancreas, liver, and gallbladder must be performed within one week of the first occurrence of any \geq Grade 3 of amylase and/or lipase.	

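### For an asymptomatic Grade 4 CK elevation with normal markers in Phase Ib Cycles 1-2, Section 6.3.1 says withhold and reduce, Table 6-4 says continue, and no text says which governs

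*Protocol*

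**What the plan says.** Three parts of the protocol bear on the same patient.

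- **DLT definition (Section 6.2.4, Table 6-3).** At Grade 4 the rule is "Any Grade 4 AEs will be considered DLTs with the exception of" short, uncomplicated neutropenia and lymphopenia or leukopenia. The exception for "CK elevation without associated muscle damage per investigator discretion" stands in the Grade 3 list only.
- **General dosing rule (Section 6.3.1).** "If a patient experiences an AE meeting the criteria for DLT as outlined in Section 6.2.4, treatment should be withheld". After recovery to Grade 1 or baseline the investigator may restart: "Following an AE meeting criteria for DLT, if a patient resumes study treatment, it should be at the next lower dose level".
- **Toxicity-specific rule (Table 6-4, CK elevation, Grade 3-4).** With normal CK-MB and troponin and creatinine up to 1.5 times baseline, the row ends "patient asymptomatic, continue treatment". Delay, and restart with MCS110 one level down, apply only when markers are abnormal or the patient has symptoms.

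Section 6.3.1 describes Table 6-4 as a summary of the modifications for drug-related toxicity. It does not say whether a table row overrides the DLT rule.

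**The concern.** An investigator facing this patient has two stated instructions and can follow only one. The event is foreseeable: the protocol treats CK elevation as a pharmacological effect of MCS110, and Section 1.2.2.2 reports elevations up to Grade 4 in healthy volunteers and in PVNS patients. In PVNS patients the maximum was generally seen at Day 28 or Day 43, and Day 28 lies inside the 42-day DLT window. The Amendment 04 rationale describes that timing as following a single dose, so carrying it over to three-weekly dosing is an assumption.

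The choice affects the patient's dosing. It also affects dose interruptions, reductions and dose intensity, which Protocol 10.4.1 lists as primary Phase Ib tolerability variables. If sites resolve the conflict differently, those summaries partly reflect how the protocol was read and not only how the drug was tolerated.

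**Working it through.** **Is there a conflict?** Take a treatment-related Grade 4 CK elevation in Cycle 1 or 2 of Phase Ib, with normal CK-MB and troponin, creatinine at most 1.5 times baseline and no symptoms.

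1. Table 6-3: Grade 4, and CK is not among the Grade 4 exceptions, so the event is a DLT.
2. Section 6.3.1: a DLT, so withhold; if resumed, next lower level.
3. Table 6-4, CK row: Grade 3-4 with all conditions met, so continue.

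Steps 2 and 3 are incompatible. At Grade 3 there is no conflict, because Table 6-3 exempts the event at step 1.

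**Do other rows share the tension?** Yes. Grade 4 neutropenia lasting 6 to 7 days falls outside the Table 6-3 exception, yet its Table 6-4 row says to "resume study treatment without dose modification, after discussion with the Novartis Medical Monitor". Grade 4 anemia also resumes without modification. For asymptomatic Grade 3-4 amylase or lipase elevation the row begins "Continue study treatment. If levels do not resolve to". CK is the clearest case because it is an expected drug effect.

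**What would the choice do to dosing?** The plan gives no figure, so this is an illustration.

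Inputs: dose levels from Table 6-2 plus the added 7.5 mg/kg level; patients per level from the Amendment 04 study status (6 + 12 + 12 + 13 + 6 + 11 = 60). SAP 2.4.1 defines relative dose intensity (RDI) as actual over planned dose intensity, which here equals cumulative dose over cumulative planned dose.

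Assumptions: six scheduled doses, two full and then four reduced (case A); or the Cycle 3 dose skipped and three reduced (case B).

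RDI (A) = (2 × full + 4 × reduced) / (6 × full). RDI (B) = (2 × full + 3 × reduced) / (6 × full).

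| Start (MCS110 mg/kg / PDR001 mg) | Patients | Next lower | Drug cut | Cut | RDI (A) | RDI (B) |
|---|---|---|---|---|---|---|
| 10/300 | 11 | 5/300 | MCS110 | 50% | 40/60 = 67% | 35/60 = 58% |
| 10/300, if 7.5 counts | (same 11) | 7.5/300 | MCS110 | 25% | 50/60 = 83% | 42.5/60 = 71% |
| 7.5/300 | 6 | 5/300 | MCS110 | 33% | 35/45 = 78% | 30/45 = 67% |
| 5/300 | 13 | 3/300 | MCS110 | 40% | 22/30 = 73% | 19/30 = 63% |
| 3/300 | 12 | 3/100 | PDR001 | 67% | 1000/1800 = 56% | 900/1800 = 50% |
| 3/100 | 12 | 1/100 | MCS110 | 67% | 10/18 = 56% | 9/18 = 50% |
| 1/100 | 6 | 0.3/100 | MCS110 | 70% | 3.2/6 = 53% | 2.9/6 = 48% |

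In case B the drug that is not reduced has RDI 5/6 = 83%. Under the continue rule RDI is 100%. From 3/300 the general rule cuts PDR001 and leaves MCS110, the drug held responsible for CK elevation, unchanged. At the other levels (60 − 12 = 48 starting patients) it cuts MCS110.

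**The case against.** The strongest reply is that a specific row beats a general rule. Section 6.3.1 sends the reader to Table 6-4 straight after telling them to withhold. The CK row names Grade 4 and sets its own marker conditions, and its split between normal and abnormal findings would lose most of its purpose at Grade 4 if the general rule always applied. This is a reasonable reading, but nothing states it. The Amendment 01 summary points the other way: after health authority feedback it listed Grade 4 CK elevation as a DLT and added instructions to reduce the dose after a DLT. A careful investigator could therefore take the general rule as controlling.

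A second reply is that, under Section 8.1.1, an asymptomatic laboratory change need not be an adverse event. This does not remove the conflict. Section 6.2.4 counts abnormal laboratory values, and Table 6-3 treats CK elevation without muscle damage as something that needs an exception.

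Three limits stand. The lower dose applies only if treatment is resumed. The Table 6-4 delay footnote, which also mentions a lower level for DLT-criteria events, applies only after a delay of more than seven days; under the continue rule there is no delay, so it adds nothing here. And by Amendment 05 escalation was complete, enrollment had closed, and the six patients still on treatment were all in Phase II.

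**Conclusion.** The contradiction is real for Phase Ib Cycles 1-2. Whether it reaches later cycles or Phase II depends on reading the DLT criteria without their two-cycle window, which the text leaves open. It is an inconsistency in dosing instructions that should be corrected, although little practical benefit remains.

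The RDI ranges (53-83%, or 48-71% with one skipped dose, against 100%) show what the choice would do to one affected patient. They rest on six scheduled doses and at most one skipped dose, and no recovery time to Grade 1 or baseline is given.

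Two stronger inferences are not supported. A reader might infer that many patients were affected. The 48 of 60 counts starting dose levels, not events, and the 15 of 52 healthy volunteers (29%) had CK elevation of any grade; no count of Grade 4 events is given. A reader might also infer that the escalation model was fed the wrong number of DLTs. Table 6-3 alone decides whether the event is a DLT, whichever dosing rule is followed. One narrow qualification: SAP 2.5.2.1.1 uses the lower dose when a patient's two doses in the first two cycles differ, so a reduction made by Cycle 2 could change the dose level at which the event is entered, but not whether it is counted.

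**What to change.** Add to Section 6.3.1:

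- Where a named-toxicity row of Table 6-4 states an explicit dosing action, as the CK row does, that row governs the patient's dosing.
- The withhold and next-lower-level rule applies to all other events meeting DLT criteria, including those under the catch-all rows for other adverse events and those whose row is silent on the dose at resumption.
- A Grade 4 CK elevation in Cycles 1-2 still counts as a DLT for the BLRM.

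The catch-all rows must be excluded by name; otherwise they would leave almost nothing for the post-DLT reduction rule to cover. The named-row clause would also settle the neutropenia, anemia and amylase/lipase rows, so the sponsor should confirm that this is intended for each.

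If the sponsor instead wants the DLT reduction rule to control, limit the continue instruction in the CK row to Grade 3. The delay footnote needs no change for this case.

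The cost is a short text edit. No new data or output is needed: SAP 2.4.1 already lists all doses with reasons for change, and SAP 2.8.3 lists laboratory values with CTC grade.

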6.2.2 Provisional dose levels

Table 6-2 describes the starting dose and the dose levels that may be evaluated during this trial.

Table 6-2 Provisional dose levels

Dose level *	Proposed dose MCS110	Proposed dose PDR001
-2**	0.3 mg/kg Q3W	100 mg Q3W
-1**	1 mg/kg Q3W	100 mg Q3W
1 (starting dose)	3 mg/kg Q3W	100 mg Q3W
2	3 mg/kg Q3W	300 mg Q3W
3	5 mg/kg Q3W	300 mg Q3W
4	10 mg/kg Q3W	300 mg Q3W

* It is possible for additional and/or intermediate dose levels to be added during the course of the study. Cohorts may be added at any dose level below the MTD in order to better understand safety, PK or PD

** Dose level -1 or -2 represent provisional dose levels and/or treatment doses for patients requiring a dose reduction from the starting dose level. No dose reduction below dose level -2 is permitted for this study

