Grade 2	Hold study treatment. Pulmonary and infection workup. Upon resolution to \leq Grade 1, may resume study treatment without dose modification
Grade 3 or 4	Discontinue study treatment.
Ocular (uveitis)	
Grade 1	Continue study treatment without dose modification. Ophthalmology consultation.
Grade 2	Hold study treatment. Urgent ophthalmology consultation. Upon resolution to \leq Grade 1 may consider resuming study treatment without dose reduction after discussion with the Novartis Medical Monitor and in consultation with ophthalmology

Toxicity	Dose Adjustment Rules*
Grade 3 or 4	Discontinue from treatment. Urgent ophthalmology consultation.
Periorbital edema	
Grade 2	Delay treatment until resolved to ≤ Grade 1. Decrease MCS110 1 dose level.
Grade 3-4	Discontinue from treatment.
Dermatology (rash)	
Grade 1	Continue study treatment without dose modification. Topical steroids, antihistamines, topical emollients
Grade 2	Consider holding study treatment. Topical or oral steroids, antihistamines. If study treatment is held and resolution to ≤ Grade 1, resume study treatment without dose modification.
Grade 3 or Grade 4	Hold study treatment. Manage per institutional practice. After resolution to ≤ Grade 1, consider resuming study treatment after discussion with the Novartis Medical Monitor.
Bullous dermatitis	Hold study treatment. Grade 1-2 bullous dermatitis: discussion with the Novartis Medical Monitor is required before considering resuming study treatment. Grade 3 bullous dermatitis: consider resuming therapy after expert consultation and documented discussion with the Novartis medical monitor. Grade 4 bullous dermatitis: discontinue study treatment.
Stevens-Johnson syndrome (SJS), or Lyell syndrome/toxic epidermal necrolysis (TEN)	Permanently discontinue study treatment.
Cardiovascular	
ECG QTc-Interval prolonged; hypertension	
Grade 3	Hold study treatment. Upon resolution to Grade ≤ 1 or baseline (hypertension, QTc) or < 30 msec difference from baseline (QTc) within ≤ 7 days, may resume study treatment without dose modification after discussion with the Novartis Medical Monitor. Baseline ECG refers to the ECG(s) collected at screening
Grade 4	Discontinue study treatment
Other cardiovascular disorders	
Grade 2 (except myocarditis)	Hold study treatment. Upon resolution to Grade ≤ 1 or baseline, may resume study treatment without dose modification after discussion with the Novartis Medical Monitor..

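### From 3 mg/kg MCS110 + 300 mg PDR001, Section 6.3.1 and Table 6-4 send a patient with a dose-limiting CK elevation to incompatible doses, with no stated precedence

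*Protocol*

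**What the plan says.** Three parts of the Protocol bear on a dose reduction.

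- **Table 6-2 (Section 6.2.2)** is the only list of dose levels, and each numbered level is an MCS110/PDR001 pair. Level 2 is "3 mg/kg Q3W 300 mg Q3W", the level below it is "1 (starting dose) 3 mg/kg Q3W 100 mg Q3W", and level -1 is "1 mg/kg Q3W 100 mg Q3W". Its footnote says "Dose level -1 or -2 represent provisional dose levels and/or treatment doses for patients requiring a dose reduction" from the starting level. It also allows further levels to be added, and 7.5 mg/kg + 300 mg was added and taken into Phase II.
- **Section 6.3.1, text:** after an AE meeting DLT criteria, "if a patient resumes study treatment, it should be at the next lower dose level". The reduction floor in the same bullet is stated as a pair.
- **Table 6-4 (Section 6.3.1):** for CK elevation of Grade 3-4 with abnormal cardiac markers, raised creatinine or symptoms, the instruction after recovery of the cardiac markers and "creatinine to Grade 1 or baseline, restart treatment. Decrease MCS110 1 dose level". For Grade 2 periorbital edema it is likewise "Decrease MCS110 1 dose level". No dose is given and PDR001 is not mentioned. A footnote adds "Treatment: refers to both study drugs, unless one has been discontinued".

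No separate sequence of MCS110 levels is given, and no text ranks the Section 6.3.1 rule against the Table 6-4 rule.

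**The concern.** A one-level reduction should lead every site to the same dose. From level 2 it does not. Stepping down the numbered levels changes only PDR001, while Table 6-4 asks for less MCS110. Two sites treating the same event could each follow a written rule and give different drugs at different doses.

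Two analyses are touched. Dose reductions and dose intensity are primary tolerability variables in Phase Ib (Protocol 10.4.1), and SAP 2.4.1 summarises them for each drug, so the same event can appear as a reduction of one drug or of the other. SAP 2.5.2.1.1 also says that if a patient's doses in the first two cycles differ, the lower dose is used in the dose-toxicity model. For a patient with a DLT in cycle 1 who resumes at a reduced dose in cycle 2, the pair entered would depend on which rule the site followed.

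**Working it through.** The plan gives no figure to reproduce. The check is to step down from every level under two readings: the next lower numbered level in Table 6-2, and the next lower MCS110 value with PDR001 held. Doses are MCS110 mg/kg / PDR001 mg, from Table 6-2 plus the added 7.5/300.

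| From | Next numbered level | Next lower MCS110, PDR001 held | Same? |
|---|---|---|---|
| 10/300 | 5/300 (7.5/300 if counted) | 5/300 (7.5/300 if counted) | yes |
| 7.5/300 (added) | 5/300 | 5/300 | yes |
| 5/300 | 3/300 | 3/300 | yes |
| **3/300** | **3/100** | **1/300** | **no** |
| 3/100 | 1/100 | 1/100 | yes |
| 1/100 | 0.3/100 | 0.3/100 | yes |
| 0.3/100 | none (floor) | none (floor) | n/a |

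Size of the split at 3/300:
- Next numbered level: MCS110 (3 - 3)/3 = 0%; PDR001 (300 - 100)/300 = 67% lower.
- Next lower MCS110: MCS110 (3 - 1)/3 = 67% lower; PDR001 0%.

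The pair 1/300 is not in Table 6-2. It appears as the optional lower-dose pancreatic group and in the Appendix 3 simulation grid, but not as a listed reduction level. The nearest listed pair with less MCS110 is 1/100, which lowers both drugs and lies two numbered levels down.

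Whether one event can fall under both rules:
- **CK elevation.** Table 6-3 treats Grade 4 events as DLTs, with exceptions that do not include CK. It exempts Grade 3 CK elevation only when there is no associated muscle damage. A Grade 4 event, or a Grade 3 event with muscle damage, that also meets the Table 6-4 conditions therefore triggers both rules. At 3/300 the Section 6.3.1 rule, read through Table 6-2, gives 3/100, and 3/100 does not satisfy Table 6-4.
- **CK elevation that is not a DLT.** Only Table 6-4 applies. Its wording points to lowering MCS110, but the accompanying PDR001 dose is not stated.
- **Grade 2 periorbital edema.** It is not among the listed Grade 2 DLTs, although the general clause on other clinically significant toxicities could reach it. The same gap applies.

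The DLT definition in Section 6.2.4 covers the first two cycles. If that window is part of the criteria cited in Section 6.3.1, the two-rule conflict is confined to those cycles; the missing pair is not.

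Exposure: the Amendment 04 study status gives 12 patients at 3/300 out of 6 + 12 + 12 + 13 + 6 + 11 = 60, and 12/60 = 20%.

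**The case against.** The best reply is that dose level is also a per-drug term. The glossary defines it for a drug, the reporting rules in Section 10 speak of levels of MCS110 and of PDR001, and Section 10.4.2.2 refers to a lower MCS110 level with PDR001 held at 300 mg. Table 6-4 names MCS110, so neither 3/100 (MCS110 unchanged) nor 1/100 (two levels down) carries out its text. The DLT bullet in Section 6.3.1 itself points to Table 6-4 for modifications, so Table 6-4 could be taken as the specific rule.

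Much of this stands. A reader might infer that Table 6-4 itself tells sites to restart at the same MCS110 dose; its wording does not support that. It does not remove the conflict. The same bullet that points to Table 6-4 goes on to require the next lower level, Section 6.2.3 uses that phrase with reference to the pairs in Table 6-2, and nothing says the specific rule prevails. Even on a per-drug reading, the pair that results from 3/300 is not listed.

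It is also fair that the trigger is narrow. CK elevations were described as asymptomatic in healthy volunteers, and an asymptomatic elevation with normal markers and creatinine does not lead to a reduction under Table 6-4. The six patients still on treatment at Amendment 05 were all in Phase II. From 7.5/300, a patient would need two reductions to reach 3/300 and a third event to meet the conflict.

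**Conclusion.** The conflict is real and narrow. At one of six provisional levels, two stated rules give incompatible doses for a CK event that is both a DLT and a Table 6-4 trigger. For other events under the same Table 6-4 instruction, no resulting pair is given. The other listed steps agree under both readings. This rests on taking the next lower level in Section 6.3.1 to mean the next numbered pair in Table 6-2.

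Stronger conclusions that a reader might draw are not supported:
- **That 20% of Phase Ib patients were affected.** Twelve of 60 counts patients who received 3/300. The number who triggered the rule is not given.
- **That efficacy would be lost at 3/100.** Sections 2.3 and 6.2.1 expect antitumor activity from PDR001 at 100 mg.
- **That tolerability would be charged to the wrong drug.** SAP 2.4.1 derives reductions from actual doses and reports reasons for each drug, so a PDR001 reduction that took place would be counted correctly with its reason shown. What the conflict can do is make the drug reduced depend on the site's reading.
- **That the planned 1 mg/kg + 300 mg pancreatic group is left without a reduction step.** Amendment 05 reports that the expansion criteria were not met and enrolment is closed.

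**What to change.** Reconcile Section 6.3.1, Table 6-2 and Table 6-4 so that each reduction instruction yields one dose pair from each treated pair, including 7.5 mg/kg + 300 mg. State which rule governs when an event meets DLT criteria and also has its own entry in Table 6-4. Which pair applies is for the clinical team to decide.

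For any patient already reduced from 3 mg/kg + 300 mg, list in the CSR the pair received and the drug reduced. Section 6.6 already requires every dose change on the Dosage Administration Record, so no new CRF field is needed.

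The cost is one short table and a precedence sentence in an amendment, plus one listing.
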